## Section 12. REMUNERATION AND PLAN FOR DISTRIBUTION

Refer to the University [Business and Financial Policies and Procedures](#) for further guidance on the compensation process and reporting requirements.

**12A. Will subjects receive inducements or rewards before, during, or after participation?**

Yes  No

If yes, complete the rest of Section 12. If no, proceed to Section 13.

**12B. Select all forms of remuneration that apply.**

Cash, please specify amount:

Check, please specify amount:

Gift Certificate, please specify amount: All participants who complete a video screening session will receive \$15 Amazon e-code. To promote the highest retention rate possible in the RCT, participants will be compensated \$25 at each assessment session. There is an additional supplemental interview that will be given to participants currently receiving the intervention and they will be paid \$15 for each supplemental interview. Although participants in Group 2 will complete two additional assessments

(week-12 and week-16), they will be compensated for these two additional assessments. Also, participants will be allowed to keep their OneClick subscription for a year free of cost.

Lottery, please specify amount: and odds:  
 Course Credit, please specify amount: and specify equivalent alternative activity:  
 Other, please specify: Amazon e-codes will be the primary form of payment, but participants can request an alternative method (cash or check).

**12C. Will payment be prorated before, during, or after participation?**

Yes, please specify how: In the event participants withdraw from the study early, they will receive payment for any assessments they have completed.  
 No

**12D. For each group of participants, describe the details of the remuneration plan, including how, when**

Payments (Amazon gift card; checks; cash) will be distributed at the end of the study, or at the end of participation, determined by a researcher. Participants will receive a check by mail or an Amazon E-code via email depending upon their preference.

**12E. The information listed above is provided on the relevant consent forms.**

Yes

## Section 13. RISKS & BENEFITS

**13A. Describe all known risks to the participants for the activities proposed, such as risks to the participants' physical well-being, privacy, dignity, self-respect, psyche, emotions, reputation, employability, and criminal and legal status. Risks must be described on consent forms.**

There are no specific physical or psychological risks associated with cognitive, psychological, or usability assessments in this research. The assessments include outcome measures that have been used previously with this population, including technology evaluations in persons with MCI, by the investigators. The primary risks of the evaluations and observations are fatigue and frustration due to the difficulty of some tasks. The potential risks for using a novel social engagement platform (small group video discussion) is hesitation in interacting with strangers.

**13B. Describe the steps that will be taken to minimize the risks listed above.**

To reduce the risks of fatigue and frustration, we will provide encouragement, scheduled breaks, and a supportive environment to make participation an interesting and beneficial experience. The events will be initiated by a host, a member of our research team. A few conversational prompts will be provided to facilitate interactions. Also, participants will have the options to only sign up for topics of their choice. Our prior research has shown that older adults form new friendships (i.e., with strangers) when they co-participate in an activity and/or share interests. OneClick, the social platform under investigation, is designed to connect people over shared interests.

**13C. Indicate the risk level.**

**No more than minimal risk**

(The probability and magnitude of harm or discomfort anticipated for participation in the proposed research are not greater in and of themselves than those ordinarily encountered in daily life or during the performance of routine physical or psychological examinations or tests).

**More than minimal risk (answer 13D)**

**13D. If you checked that the research is more than minimal risk, describe the provisions for monitoring the data to ensure the safety of subjects, such as who will monitor data and how often, what criteria will be used to stop the research, etc.****13E. Describe the expected benefits of the research to the subjects and/or to society.**

The findings from this study will have major implications on the launch and commercialization of a novel Internet-based social engagement platform for older adults with and without MCI. Furthermore, by making the platform accessible for these specific user groups, OneClick also will become more accessible to other, non-impaired and younger, users. This is the promise and benefit of universal, user-centered design. The platform could offer an easy, affordable (i.e., free) socialization avenue especially to people living in remote, socially-isolated areas and to those feeling socially isolated and lonely. The direct benefits to the participants and society outweigh any potential risks incurred through participation.

**13F. Weigh the risks with regard to the benefits. Provide evidence that benefits outweigh risks.**

We have taken precautions to decrease foreseeable potential risks to the participants as a result of their participation in this study. Overall the risks of interacting with the OneClick system, participating in the interview and completing the questionnaires should be minimal. A potential benefit for the participants is social and cognitive stimulation. These benefits outweigh the potential risks, which are minimal to begin with and will be further minimized by the proposed research.

**Section 14. INFORMED CONSENT PROCESS TO INCLUDE: WAIVERS, ASSENTS, ALTERATIONS, ETC.****14A. Indicate all that apply for the consent/assent/parental permission process.**

Written informed consent (assent) with a document signed by  
     adult subjects  parent(s) or guardian(s)  adolescents aged 8–17 years

Waiver of Documentation (signature) of Informed Consent (*include the relevant [Waiver Form](#)*)  
     adult subjects  parent(s) or guardian(s)  adolescents aged 8–17 years

Waiver of Informed Consent (*include the relevant [Waiver Form](#)*)  
     adult subjects  parent(s) or guardian(s)  adolescents aged 8–17 years

Alteration of Informed Consent (*include the relevant [Alteration Form](#)*)  
     adult subjects  parent(s) or guardian(s)  adolescents aged 8–17 years

**14B. List all researchers who will obtain consent/assent/parental permission from participants.**

[name], [name], [name], [name], [name] (For more information of the researchers, please see attached research team form).

**14C. Describe the method for obtaining consent/assent/parental permission.** Informed consent will be obtained online before any testing is undertaken. Details related to the study will be discussed at length. Any questions pertaining to the study and participation will be answered. The online informed consent process will be administered over REDCap with a research team member and signed electronically. Participants will receive a copy of the signed document for their records (either electronically or a paper version mailed to their home).

**14D. Describe when consent/assent/parental permission will be obtained.** Informed consent for the video screening will be obtained before the video screening session begins. Informed consent for the RCT will be obtained before the baseline assessment session begins.

**14E. Will participants receive a copy of the consent form for their records?**

Yes  No, if no, explain:

**14F. Indicate factors that may interfere or influence the collection of voluntary informed consent/assent/parental permission.**

No known factors  
 Research will involve students enrolled in a course or program taught by a member of the research team  
 Research will involve employees whose supervisor(s) is/are recruiting participants  
 Participants have a close relationship to the research team  
 Other, specify any relationship that exists between the research team and participants:

If applicable, describe the procedures to mitigate the above factors.

**14G. Copies of the consent form(s) are attached.**  Yes  Not applicable

**14H. Will this project be registered as a clinical trial?**  Yes  No

If yes, effective January 21, 2019, an informed consent form must be posted on the Federal Web site after the clinical trial is closed to recruitment, and no later than 60 days after the last study visit.

## Section 15. DEVICES & DRUGS

**Indicate if your research includes any of the following.**

Equipment [Researchers collecting physiological data, not testing the device]  
*(include Appendix A, the [Research Equipment Form](#))*  
 Devices [Researchers planning to test devices on human subjects]  
*(include Appendix B, the [Device Form](#))*  
 Materials of Human Origin  
*(include Appendix C, the [Biological Materials Form](#))*  
 Drugs and Biologics  
*(include Appendix D, the [Drug and Chemical Usage Form](#))*

MRI AT BIC To use the [Beckman Institute Biomedical Imaging Center \(BIC\)](#) in human subject's research, you must obtain prior approval from the BIC [contact]; [[contact]](mailto:[contact])) and use BIC-approved screening and consent forms. Attach:

BIC approval  BIC screening form  BIC consent form

## Section 16. CONFIDENTIALITY OF DATA & PRIVACY OF PARTICIPATION

**16A. How is participant data, records, or specimens identified when received or collected by researchers? Identifiers include, but are not limited to, name, date of birth, email address, street address, phone number, audio or video recordings, and SSN.**

No identifiers are collected  
 Direct identifiers are collected  
 Indirect identifiers (e.g. a code or pseudonym used to track participants);  
Does the research team have access to the identity key?  Yes  No

**16B. Select all methods used to safeguard research records during storage:**

Written consent, assent, or parental permission forms are stored separately from the data  
 Data is collected or given to research team without identifiers  
 Data is recorded by research team without identifiers  
 Direct identifiers are removed from collected data as soon as possible  
 Direct identifiers are deleted and no identity key exists as soon as possible  
 Participant codes or pseudonyms are used on all data and the existing identity key is stored separately from the data  
 Electronic data is stored in a secure, [UIUC-approved location](#), please specify PHI Box  
 Hard-copy data is stored in a secure location on UIUC's campus, please specify  
 Other, please specify:

**16C. How long will identifiable data be kept?** Electronic versions of the data will be archived on PHI box

**16D. Describe provisions to protect the privacy interests of subjects.** Information about this research study will remain confidential unless we are required by law to release it. Electronic copies of the signed consent forms will be stored on PHI box. All participants will be assigned a participant code that is not related to their personal information in any way. This participant code will be used for all data collection. There will be one master sheet linking participant name to participant code. This sheet will be electronically stored on the PHI box with restricted access to the research team. All electronic copies of the data will be stored by study ID in the PHI box that only the research team has access to including the audio recordings. Once audio files are uploaded to the PHI box, these files will be deleted from the initial recording device. Strict security will be maintained to access the PHI box. No identifying information will be mentioned in any presentations or publications. Similar procedures at these study sites have proven to effectively prevent loss of confidentiality.

**16E. Describe the training and experience of all persons who will collect or have access to the data.**

Data collection will be carried out by trained personnel and access to study data will be limited to researchers directly involved with this research study who have been trained in methods to protect the

confidentiality, including IRB CITI training requirements. Workshops are held to ensure that all individuals involved in research keep their certification current.

## Section 17. DISSEMINATION OF RESULTS

**17A. List proposed forms of dissemination (e.g. journal articles, thesis, academic paper, conference presentation, sharing within industry, etc.).**

Results may be disseminated in the following forms: journal articles, thesis or academic papers, conference proceedings and presentations, and technical reports.

**17B. Will any identifiers be published, shared, or otherwise disseminated?**  Yes  No

If yes, does the consent form explicitly ask consent for such dissemination, or otherwise inform participants that it is required in order to participate in the study?  Yes

**17C. Do you intend to put de-identified data in a data repository?**  Yes  No

If yes, explain how data will be de-identified.

We will use subject ID to substitute the real name of the participants.

Identifiers: NCT05380180

Brief Title: Enhancing Quality of Life for Older Adults With and Without Mild Cognitive Impairment (MCI) Through Social Engagement Over Video Technology

Document Date: Sept 4, 2023

Statistical Analysis Plan

To measure the main effects of the intervention on primary and secondary outcomes, irrespective of the cognitive status, the OneClick intervention Group will be compared to the Waitlist group at (i) mid-assessment (4 weeks) compared with the baseline assessment, and (ii) post-assessment (8 weeks) compared with baseline assessment. In addition, we will perform a separate analysis of covariance with age and cognitive ability (MoCA and Logical Memory - Delayed Recall) as covariates. We plan to implement an intent-to-treat analysis where all participants who were allocated to either the intervention or waitlist group will be included in the analysis, regardless of the number of sessions attended or their completion of assessments.

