5. Baseline Assessment: Baseline assessment will include participant characterization measures and intervention outcome measures. The session will last approximately one hour.
6. Randomization process: The randomization process is designed to achieve appropriate generation of the random allocation sequence and concealment of the allocation sequence. A researcher who is not involved in phone screening, video screening, or informed consent will generate the randomization list prior to the screening of the first person for the randomized, controlled trial. The randomization list will use computer-generated random numbers. The randomization list will be stratified with random permuted blocks. The stratification variable will be Mild Cognitive Impairment (MCI present versus absent). MCI will be defined by a MoCA score of 20-25. The block size will vary randomly between 4 and 6. Research personnel who perform phone screening, video screening, informed consent, or assessments will not be able to access the randomization list. After a potential participant has completed phone screening and video screening, has fulfilled all inclusion criteria, has demonstrated no exclusion criteria, has provided documented informed consent, and has completed baseline assessment, the researcher will unconceal the randomization assignment for the intervention: Group 1 (intervention first) versus Group 2 (intervention later). After assignment, the participant and the researcher who performed informed consent will not be blinded to group allocation.
7. Participants in Group 2 will be told they will begin the intervention 8 weeks later and in the meantime will be asked to complete assessments at 4 and 8 weeks after joining the study but before beginning the video chat participation. Participants in Group 1 will be given information about the general research expectations over the next 8 weeks and will be invited to sign up for a technology training session to learn how to use the OneClick system.

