## Section 9. SUBJECT ENROLLMENT GOAL & EQUITABLE SELECTION OF SUBJECTS

**9A. For each performance site, indicate the estimated total number of participants.**

Performance Site	# Male	# Female	Total
#1 UIUC	53	53	106
#2 CJE Senior Life	35	35	70

#3			
TOTALS	88	88	176
If additional performance sites are included on an attachment, check here: 			
9B. Select all participant populations that will be recruited.			
Age:			
 Adults (18+ years old)  Minors ( $\leq$ 17 years old)  Specific age range, please specify : 65 and older			
Gender:			
 No targeted gender (both men and women will be recruited/included)  Targeted gender, please indicate :  Men/boys  Women/girls  Other, please specify :			
Race/Ethnicity:			
 No targeted race or ethnicity (all races and ethnicities will be recruited/included)  Targeted race or ethnicity, please specify :			
College Students:			
 No targeted college population  UIUC general student body  Targeted UIUC student population, provide the instructor or course information, name of the departmental subject pool, or other specific characteristics :  Students at institution(s) other than UIUC, please specify :			
Any research with students on UIUC's campus needs to be registered with the Office of the Dean of Students .			
Other:			

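### Randomisation is stratified by MCI, but the SAP lists no stratum term for the main comparison; if that comparison is run unadjusted, its tests may be slightly conservative

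*SAP*

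**What the plan says.** Protocol section 7F, step 6 (Randomization process), states: "The randomization list will be stratified with random permuted blocks". It names one factor: "The stratification variable will be Mild Cognitive Impairment (MCI present versus absent"). The stratum is set by a single score: "MCI will be defined by a MoCA score of 20-25". On blocks it says: "The block size will vary randomly between 4 and 6".

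The SAP is one paragraph. For the main effects on primary and secondary outcomes it says that "irrespective of the cognitive status, the OneClick intervention Group will be compared to the Waitlist group", at week 4 and at week 8, each against baseline; the second contrast is the "post-assessment (8 weeks) compared with baseline assessment". It names no model or test for this comparison and lists no covariate. It then adds: "we will perform a separate analysis of covariance with age and cognitive ability (MoCA and Logical Memory - Delayed Recall) as covariates". The MCI stratum as a factor appears in neither analysis, and the SAP does not say which of the two takes precedence.

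**The concern.** Permuted blocks within MCI strata hold the two arms to almost the same MCI mix. Any outcome difference between people with and without MCI therefore contributes almost nothing to chance differences between arms, and the true sampling variance of the treatment difference falls. A comparison without the stratum still counts that between-stratum variation as error. Its reported standard error is then larger than the true one, its confidence interval is wider than it need be, and its test rejects less often than its nominal level. What is at stake is some of the precision that the stratified design was set up to provide. The treatment estimate itself is not affected.

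**Working it through.** There is no figure in the plan to reproduce. The documents give an enrolment goal but no alpha, power, effect size or SD.

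**Inputs from the documents**
- Total 176 (Protocol section 9A). The 88/88 split printed there is male/female, not arms.
- One stratification factor (MCI), with permuted blocks of 4 or 6 (Protocol section 7F, step 6).
- Main comparison pooled over cognitive status, at weeks 4 and 8 against baseline (SAP).

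**Assumptions, because the documents are silent**
- 1:1 allocation, so n = 88 per arm; half with MCI; no dropout; two-sided alpha 0.05.
- Outcome SD of 1, so results are in SD units.
- True effect d = (1.960 + 0.842) × √(2/88) = 0.422 SD, which gives a nominal 80% power.
- R², the share of variance in the analysed outcome explained by MCI, from 0 to 0.10. With half in each stratum, R² = 0.25 × gap², where gap is the MCI difference in SD units.

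**Formulas**
- SE reported without the stratum: √(2/88) = 0.151.
- True SE, which is also the SE reported with the stratum: √(2(1 − R²)/88).
- Overstatement of the SE: 1/√(1 − R²).
- Actual type I error without the stratum: 2 × [1 − Φ(1.960/√(1 − R²))].
- Actual power without the stratum: Φ((0.422 − 1.960 × 0.151)/true SE).
- Power with the stratum: Φ(0.422/true SE − 1.960).

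**Worked line, R² = 0.10.** True SE = √(1.8/88) = 0.143. Overstatement = 1/√0.90 = 1.054. Type I error = 2 × [1 − Φ(2.066)] = 3.9%.

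| R² | Gap (SD) | SE reported, no stratum | True SE | SE too large by | Type I error | Power, no stratum | Power, with stratum |
|---|---|---|---|---|---|---|---|
| 0 | 0 | 0.151 | 0.151 | 0% | 5.0% | 80.0% | 80.0% |
| 0.01 | 0.20 | 0.151 | 0.150 | 0.5% | 4.9% | 80.1% | 80.4% |
| 0.02 | 0.28 | 0.151 | 0.149 | 1.0% | 4.8% | 80.2% | 80.8% |
| 0.05 | 0.45 | 0.151 | 0.147 | 2.6% | 4.4% | 80.6% | 82.0% |
| 0.10 | 0.63 | 0.151 | 0.143 | 5.4% | 3.9% | 81.2% | 84.0% |

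At R² = 0.10 the term is worth 84.0 − 81.2 = 2.8 points of actual power. Against the nominal 80% the figure is 4.0 points; the smaller figure is the like-for-like comparison.

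**Check by simulation.** 10,000 trials per scenario, blocks of 4 and 6 within two strata, least squares with and without the MCI term:
- R² = 0: rejection under no effect 5.0% without and 4.9% with; power 79.7% and 79.7%.
- R² = 0.05: 4.5% and 4.9%; power 80.1% and 81.5%.
- R² = 0.10: 3.9% and 4.9%; power 80.6% and 83.4%. The mean reported SE without the term is 0.151, against an empirical SD of 0.144.

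The simulation agrees with the formulas in direction and size.

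**The case against.** Three objections have weight.

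1. **The SAP does not exclude a stratum term.** A reader might infer from its wording that MCI is deliberately left out of the main model. The documents do not support that. No model is named, and the phrase about cognitive status fits a pooled main effect, which a stratum-adjusted difference also is. What stands is that a SAP listing covariates for one analysis and none for the other would, followed as written, most naturally be run unadjusted.

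2. **The comparison is against baseline.** If change scores are analysed, a stable MCI difference in level cancels, and only a different change by MCI status matters. A change-score gap of 0.1 or 0.2 SD (assumed) gives R² = 0.25 × 0.01 = 0.0025 or 0.25 × 0.04 = 0.01. The SE is then overstated by 0.1% or 0.5%, and type I error is 4.97% or 4.89%. This stands in full: nothing in the documents shows that the loss exceeds this, so a flat statement that power is lost would go too far.

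3. **The separate ANCOVA already carries MoCA.** MoCA is the score that defines the stratum, so if the outcome follows it roughly linearly, that analysis recovers much of the precision. It does not change the intervals and p-values of the main comparison, which is presented first and on its own.

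**Conclusion.** The point holds in a conditional and limited form. Randomisation is stratified by MCI and the main comparison lists no stratum term. If it is run unadjusted, and to the extent that MCI predicts the analysed change from baseline, its standard errors are somewhat too large and its tests conservative. For R² of 0 to 0.10, under the assumptions above, the overstatement is 0% to 5%, type I error runs from 5.0% down to 3.9%, and up to about 3 power points are lost like for like (about 4 against a nominal 80%). If change differs little by MCI, the effect is near zero.

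A reader might go further and conclude that the main result would be invalid. It would not: there is no bias, and the error never inflates false positives. This is a minor calibration and efficiency issue.

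**What to change.** State in the SAP that the week-4 and week-8 main comparisons include the randomisation stratum (MCI present or absent, as used for randomisation) as a fixed factor. Report the stratum-adjusted pooled difference with its 95% confidence interval. The wording about use at randomisation matters because Protocol section 10A adds memory complaints and absence of dementia to the MCI group criteria, whereas section 7F defines the stratum by MoCA alone. The result remains a pooled main effect, as the SAP intends.

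The cost is one sentence and one degree of freedom (173 residual instead of 174, with 176 analysed). No new data are needed, because the stratum is known at randomisation. If MCI turns out to be unrelated to the outcome, almost nothing is lost.

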10. Week-4 assessment: 4 weeks after being placed into Group 1 or Group 2, participants will be contacted to schedule a week-4 assessment. Participants in both groups will complete measures related to social connectedness, loneliness, isolation, and quality of life. Group 1 will additionally complete measures related to system usability and perceived enjoyment of the OneClick system. This assessment session will take approximately 1 hour will be administered by a blinded assessor remotely over video or phone. Participants will be informed at the beginning of the assessment not to reveal their group assignment. Both groups will receive \$25 for this session. For Group 1 only, an additional short, semi-structured interview will be administered over video or phone by an unblinded assessor. This will focus on ease of use, usefulness, enjoyment, satisfaction with the topics and conversation, suggestions for updates, and perceptions of social connectedness and will take 30-45 minutes. The interviews will be audiotaped and transcribed verbatim. Group 1 will receive \$15 for completing the interview.

11. After this week-4 assessment, a research team member will contact participants in Group 1 to address any questions and issues related to the intervention to help participants remain engaged in the next 4-weeks of intervention.
12. Week-8 assessment: 8 weeks after being placed into Group 1 or Group 2, participants will be contacted to schedule a week-8 assessment. Each group's assessment sessions and compensation will be identical to week-4 assessment. This ends Group 1 participation in the study. They will receive a study debriefing and thanked for their time.
13. After the week-8 assessment, a research team member will contact participants in Group 2 to schedule their technology training session (described in step #8).
14. Group 2 will now begin 8 weeks of video-chat intervention

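### For the scales given to both groups, the SAP names no model for the main comparison and its ANCOVA leaves out the outcome's own baseline score; the cost is precision, not validity

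*SAP*

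**What the plan says.** The SAP is one paragraph with two analyses.

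- **Main comparison.** OneClick against waitlist at two visits: "i) mid-assessment (4 weeks) compared with the baseline assessment, and (ii) post-assessment (8 weeks) compared with baseline assessment". No model, response variable or covariate is given.
- **Second analysis.** "we will perform a separate analysis of covariance with age and cognitive ability", where cognitive ability means MoCA and Logical Memory delayed recall. The response is not stated, and the outcome's own baseline score is not among the covariates.

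The analysis set is everyone allocated, "regardless of the number of sessions attended or their completion of assessments". No method for incomplete assessments is named.

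The protocol shows that the missing covariate will exist. Under 7F step 5, "Baseline assessment will include participant characterization measures and intervention outcome measures". Under step 6, allocation is revealed only after the participant "has completed baseline assessment, the researcher will unconceal the randomization assignment". Step 6 also sets the stratum: "The stratification variable will be Mild Cognitive Impairment (MCI present versus absent", defined by a MoCA score of 20 to 25.

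Step 10 separates two kinds of measure. At week 4, "Participants in both groups will complete measures related to social connectedness, loneliness, isolation, and quality of life", and "Group 1 will additionally complete measures related to system usability and perceived enjoyment of the OneClick system". Step 12 repeats this at week 8. The point concerns only the first kind. Usability and enjoyment have no waitlist comparator in the first 8 weeks.

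**The concern.** In a randomised comparison of a scale measured before and after, the outcome's own baseline is usually the most useful covariate. The SAP adjusts for age and two cognitive measures, neither of which is among the follow-up domains in 7F step 10, so they do not stand in for baseline loneliness, isolation, connectedness or quality of life. A precision gain that needs no new data may be left unused. Because the main model is not named, the analyst would also have to choose it later.

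Two smaller gaps sit in the same paragraph. Weeks 4 and 8 stand side by side with no primary visit. And the promise to include everyone allocated has no model behind it, while the protocol has a rule that removes some participants (7F step 9).

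**Working it through.** **Inputs.** Total enrolment is 176 (Protocol 9A). The visible text gives no allocation ratio, alpha, power, SD, correlation, effect size or loss rate, so 176 cannot be reproduced from stated inputs. Assumed here: 88 per group, two-sided 0.05, 80% power, SD s equal at all visits, and a baseline to follow-up correlation rho from 0.3 to 0.9. The variance ratios in steps 1 and 2 depend only on rho and the equal-SD assumption (step 2 also on what the listed covariates explain), not on 88 or alpha.

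**1. Main comparison read as a change score, no missing data.**

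- Variance of the difference in mean change: 2(1−rho)s² × 2/88
- Variance with the outcome's baseline as covariate: (1−rho²)s² × 2/88
- Ratio: (1−rho²) / [2(1−rho)] = (1+rho)/2, which never exceeds 1
- Detectable effect in SDs: (1.960+0.842) × √(2/88) × √v = 0.422 × √v, with v = 2(1−rho) or 1−rho²

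| rho | ratio | 176 act like (176/ratio) | detectable, change score | detectable, adjusted |
|---|---|---|---|---|
| 0.3 | 0.65 | 271 | 0.500 | 0.403 |
| 0.5 | 0.75 | 235 | 0.422 | 0.366 |
| 0.7 | 0.85 | 207 | 0.327 | 0.302 |
| 0.9 | 0.95 | 185 | 0.189 | 0.184 |

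**2. Separate ANCOVA, if it models the follow-up score.** If age, MoCA and Logical Memory explain nothing, adding baseline multiplies the residual variance by 1−rho²: 0.91, 0.75, 0.51, 0.19. This is the largest possible gain. Suppose instead that they explain 20% of the score at each visit through the same linear predictor (assumed). The partial correlation is then (rho−0.2)/0.8 = 0.125, 0.375, 0.625, 0.875. One minus its square is 0.98, 0.86, 0.61, 0.23.

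**3. Incomplete assessments.** Assume 20% are lost by week 8, half of them before week 4, equally in both arms, with equal correlation between visits. The patterns are baseline only 10%, baseline and week 4 10%, complete 80%. A week-8 regression on baseline uses 0.80 × 176 ≈ 141 people. A mixed model with baseline, week 4 and week 8 as responses and a common baseline mean uses all 176. From the generalised least squares information matrix, the variance of its week-8 contrast relative to that regression is 0.994, 0.988, 0.981, 0.975 at rho 0.3, 0.5, 0.7, 0.9. That is a gain of 0.6% to 2.5%.

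**4. Two visits.** If success at either visit counted, the error per outcome would be 1 − P(|Z₁|<1.96 and |Z₂|<1.96). For test correlations 0.3, 0.5, 0.7, 0.9 this is 9.5%, 9.1%, 8.3%, 7.0%. With equal correlation between visits, the two change scores have covariance (1−rho)s² and variance 2(1−rho)s², so their tests correlate 0.5 at any rho. Hence 9.1% is the figure that fits the change-score reading.

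**The case against.** The strongest reply is that the SAP is silent on the model rather than committed to a poor one. Comparing each visit with baseline also fits a baseline-adjusted contrast, for which the loss in step 1 is nil. It fits a group-by-visit mixed model too, which does not discard people who miss week 8. This stands: the figures in step 1 price one reading, and the certain fact is that no model is named. It does not answer the second analysis, whose covariate list is explicit and lacks the outcome's baseline.

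It is also fair that the size depends on an unknown rho. At 0.7 to 0.9 the detectable effect moves only from 0.327 to 0.302 and from 0.189 to 0.184 SD.

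Three stronger readings are tempting, and the documents do not support them.

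- **That the comparison is biased or ignores baseline.** A change-from-baseline contrast is valid under randomisation, and baseline enters through it.
- **That the error rate is inflated.** Each visit's test keeps its own level. Inflation needs a rule that success at either visit counts, and no visible text states one. The eight-week aim in Protocol 6A describes duration and does not settle the ranking either.
- **That a mixed model is needed, or that a fifth of the sample is wasted.** The 20% loss is assumed, and step 3 shows that the baseline covariate alone brings nearly all the gain.

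The removal rule in 7F step 9 follows missed OneClick sessions. In the first 8 weeks it can act only on Group 1. Step 3 assumes the same loss in both arms, so it does not represent that pattern.

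The MCI stratum is partly handled already, since the separate ANCOVA includes MoCA. Finally, part of the protocol file and the attached funding proposal (4D) were not available, and a model or primary visit may be named there.

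**Conclusion.** The point holds for the visible text and is worth acting on, as a matter of efficiency and pre-specification. The main comparison has no named model, and the separate ANCOVA omits a baseline score that is collected before allocation is revealed. It applies to social connectedness, loneliness, isolation and quality of life.

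Under equal SDs, adjusting a change-score comparison cuts its variance by 35% at rho 0.3 and by 5% at rho 0.9, and it is never less precise. If the ANCOVA models the follow-up score, the variance falls to between 0.91 and 0.19 of its present value when the listed covariates explain nothing, and by less when they explain something. If the main comparison is already baseline-adjusted, it loses nothing. All these sizes are illustrative.

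The unnamed primary visit is a secondary point. It becomes an error-rate problem only under an either-visit rule.

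**What to change.** For the scales given to both groups, the SAP should:

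- state the model for the group comparison at weeks 4 and 8, with the outcome's own baseline score and the MCI randomisation stratum as covariates;
- keep the unadjusted comparison and the age, MoCA and Logical Memory model as sensitivity analyses;
- say how participants with incomplete assessments enter. A mixed model of both visits is acceptable, with its missing-at-random assumption stated. Because the removal rule acts only on Group 1 in the first 8 weeks, add a sensitivity analysis for arm-dependent loss;
- state which visit is primary, or give a rule for the two tests.

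The cost is SAP wording, since the variables are already collected. The price is a stronger reliance on missing at random if the mixed model is used, and one visit losing equal standing. The SAP is dated Sept 4, 2023 and Protocol 7C runs the study to August 1, 2024, so timing matters: fix the change before outcome data by group are seen, or label it post hoc.
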